**Palatal Wound Healing Evaluation After
Application of Platelet Rich Fibrin Versus 0.2%
Hyaluronic Acid Dressings
(Randomized Controlled Clinical Trial)**

Methodology

Date: 12/5/2020

Sample selection and assignment:

Thirty patients (16 females and 14 males) who were candidates for free gingival grafting surgery participated in this prospective clinical trial.

The subject were recruited consecutively from the outpatient clinic of Oral Medicine, Periodontology, oral Diagnosis and Radiology Department, Faculty of Dentistry, Ain Shams University .The purpose of the study was explained to all patients and an informed consent was signed before the conduction of the study. The proposal was presented to the faculty of Dentistry Ain Shams University Research Ethics committee and was approved before starting the research with number (566). Also the study was registered in clinical trial registration site (NCT).

Patient selection:

Inclusion Criteria:

- Patients who were indicated for soft tissue augmentation with free gingival graft for mucogingival surgery or for implant therapy.

Material and Method

- Age range (20-50) years.
- Good patient compliance with the plaque control instructions following initial therapy.

Exclusion criteria:

- Presence of systemic diseases which could influence the outcome of the therapy.
(American Society of Anesthesiologists I; ASA I)
- Smoker patients.
- Pregnant and lactating females.
- Vulnerable group of patients (prisoners, handicapped, decisionally impaired individuals).

Grouping Criteria:

The study consisted of three groups; the number of patient in each group was determined by sample size calculation based upon the results of *Yildirim et al. 2017*. Using alpha level of 0.05 (5%) and β level of 0.20 (20%) i.e. power = 80%; the estimated minimum required sample size was approximately 10 cases in each group. Patients were randomly selected using computer generated randomization (www.randomizer.org). Allocation concealment was achieved using a sealed coded opaque envelope containing treatment of the subject

Group I(10 patients):

Patients received platelet rich fibrin as a palatal dressing after free gingival graft harvesting.

Group II(10 patients):

Patients received hyaluronic acid* gel 3-4 times per day as a palatal dressing after free gingival graft harvesting.

Group III(10 patients) (Control group) :

Patients received gel foam as a palatal dressing after free gingival graft harvesting

*Gengiegel 0.2% oral gel 20ml Riceerfarma Milano Italy.

III- Assessments:

1-Clinical parameters:

- Subjective assessment**

-Patients were asked to assess their pain sensation and bleeding at 1st, 3rd, 7th 14th, 21st and 30th days using the visual analogue scale (VAS). The visual analogue scale score by Price et al 1983 for pain ranged from 0 (no pain) to 10 (severe pain), while bleeding was scored as 0(not present) and 1(present) (***Price et al.1983***).

- Objective assessment**

-The Healing index scale by ***Landry et al.1988*** was used to assess the palatal wound healing, where in this index tissue color, response to palpation, presence of granulation tissue presence of suppuration and epithelization of the incision margin were recorded.

-The color of the palatal mucosa was assessed by comparing it to the adjacent and opposite side by taking pictures and using the image J program at 3rd, 7th, 14th, 21st and 30th days (***Pei-Nan et al.2012***).

- The thickness of the palatal mucosa was measured preoperative and 4 weeks postoperative by a graduated periodontal probe.

Material and Method

[figure not shown]

Fig (1): Palatal thickness measurements at 3 different points the middle of 1st, 2nd premolar and 1st molar 7mm from the gingival margin

IV-Surgical protocol:

A) Pre surgical procedures

Scaling and root planning was done; oral hygiene instructions was given to the patient to follow them.

B) Surgical procedures

Group 1:

1. Anesthesia (Articaine HCL 4% containing epinephrine at a concentration of 1:100,000)[†] was administrated at to the palate where a free gingival graft was harvested.
2. Just prior to surgery a 10 ml intravenous blood was obtained from the median antecubital vein of the patient in order to be divided into two 5 ml glass tubes[‡] without additives to be [§]centrifuged immediately at 2700 revolutions per minute for 12 minutes or in one 10 ml glass test tube without additives were centrifuged immediately at 3000 revolutions per minute for 10 minutes at room temperature.

[†] Artinibsa 4% cartouches de 1.8ml ,inibisa dental.

[‡] Dry Vacutube, Biocon®, Brazil

[§] PRF CENTRIFUGE (Duo machine), UNSPSC code 41100000 (Ostralos Ltd, New Zealand)

Material and Method

3. Coagulation started immediately and three parts quickly appear in the tube: a packed red blood cell at the bottom, acellular plasma at top and the PRF clot in between.
4. The PRF clot was removed from the tube using sterile tweezers, separating it from the RBC base by using a lancet. It was compressed between two sterile glass slabs and wrapped within sterile gauze moistened with saline.
5. The thickness of the palatal tissue was measured at three different points; each point was located at the middle of 1st, 2nd premolar and 1st molar 7mm from the gingival margin.
6. Free gingival graft was harvested from the palate and its thickness was measured.
7. The PRF membrane was placed as a palatal dressing and fixed in place by X suture using 5-0 polypropylene**.

** Assut Sutures, non Absorbable (Polypropylene) 5-0 USP, braided violet coated 3/8 rev.cutt.17mm, AM trading, Switzerland

Group 2:

1. Anesthesia (Articaine HCL 4% containing epinephrine at a concentration of 1:100,000)^{††} was administrated at to the palate where a free gingival graft was harvested.
2. The thickness of the palatal tissue was measured at three different points; each point was located at the middle of 1st, 2nd premolar and 1st molar 7mm from the gingival margin.
3. Free gingival graft was harvested from the palate and its thickness was measured.
4. Gel foam was cut according to the graft's dimensions to act as a carrier for the hyaluronic acid^{‡‡}that was used as a palatal dressing.
5. Gel foam was fixed in place using X suture using §§5-0 polypropylene.

^{††}Artinibsa 4%cartouches de 1.8ml ,inibisa dental.

^{‡‡}Gengigel 0.2% oral gel 20ml Riceerfarma Milano Italy.

§§ Assut Sutures, non Absorbable (Polypropylene) 5-0 USP, braided violet coated 3/8 rev.cutt.17mm, AM trading, Switchezland

Group 3:

1. Anesthesia (Articaine HCL 4% containing epinephrine at a concentration of 1:100,000)^{***} was administrated at to the palate where a free gingival graft was harvested.
2. The thickness of the palatal tissue was measured at three different points; each point was located at the middle of 1st, 2nd premolar and 1st molar 7mm from the gingival margin.
3. Free gingival graft was harvested from the palate and its thickness was measured.
4. Gel foam was cut according to the graft's dimensions and used as a palatal dressing.
5. Gel foam was fixed in place using X suture using 5-0 polypropylene^{†††}.

^{***} Artinibsa 4% cartouches de 1.8ml ,inibisa dental.

^{†††} Assut Sutures, non Absorbable (Polypropylene) 5-0 USP, braided violet coated 3/8 rev.cutt.17mm, AM trading, Switchezland

Material and Method

V-Postoperative care:

- Oral hygiene instructions was given , antibiotic (Augmentin^{†††} 1 gm every 12 hours, metronidazole^{§§§} 500 mg every 12 hours) , anti-inflammatory and analgesics(Brufen^{****} 400 every 12 hours) was prescribed for the patient and instructed to avoid brushing at the surgical site only rinsing with hot saline mouthwash.
- Patient was recalled for assessment and follow up, sutures was removed after 1 week.

^{†††} Augmentin 1gm,Medical union pharmaceuticals(MUP) Egypt under license from ,Glaxosmithkline

^{§§§}Flagyl 500 mg, sanofi Aventis Egypt under license of sanofi Aventis French

^{****} Brufen 400mg, Al kahira pharm. and chem.Ind.Co. under license from abbott laboratories

VI-Postoperative evaluation and assessment:

- Patients were asked to assess their pain sensation and bleeding at 1st, 3rd, 7th 14th, 21st and 30th days using the visual analogue scale (VAS). The visual analogue scale score by Price et al 1983 for pain ranged from 0 (no pain) to 10 (sever pain), while bleeding was scored as 0(not present) and 1(present).
- The Healing index scale by *Landry et al. 1988* was used to assess the palatal wound healing, where in this index tissue color, response to palpation, presence of granulation tissue presence of suppuration and epithelization of the incision margin were recorded.
- The color of the palatal mucosa was assessed by comparing it to the adjacent and opposite side by taking pictures and using the image J program at 3rd,7th, 14th, 21st and30th days.
- The thickness of the palatal mucosa was measured preoperative and 4 weeks postoperative by a graduated periodontal probe.

IV-Statistical analysis:

Categorical data were presented as frequencies and percentages and were analyzed using chi square test. Numerical data were tested for normality using Shapiro-Wilk test and were presented as mean and standard deviation values. Parametric data were analyzed using one-way ANOVA followed by Tukey's post hoc test for intergroup comparisons and one-way repeated measures ANOVA followed by Bonferroni post hoc test for intragroup comparisons. Non-parametric data were analyzed using Kruskal-wallis test followed by pairwise comparisons utilizing Mann Whitney U test with Bonferroni correction for intergroup comparisons and Friedman's test of repeated measures followed by multiple pairwise comparisons utilizing Wilcoxon signed-rank test with Bonferroni correction for intragroup comparisons. The significance level was set at $p \leq 0.05$ within all tests. Statistical analysis was performed with IBM® SPSS® Statistics Version 26 for Windows.

® IBM Corporation, NY, USA.

®SPSS, Inc., an IBM Company.

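### Does the 80% power statement have to be rewritten because it does not say whether it covers the corrected PRF-versus-hyaluronic-acid comparison?

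*Protocol*

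**What the plan says.** The Grouping Criteria section of the protocol gives the justification in two sentences. The first names the source: "the number of patient in each group was determined by sample size calculation based upon the results of" a cited 2017 study. The second gives alpha 0.05 and beta 0.20 and ends: "power = 80%; the estimated minimum required sample size was approximately 10 cases in each group". Three groups of 10 follow (PRF, HA, and gel foam as control), 30 patients in all. The section does not say which result of the cited study was used.

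The title sets PRF against 0.2% HA: "Application of Platelet Rich Fibrin Versus 0.2"%.

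No outcome is called primary. The III- Assessments section lists five. Pain and bleeding share one schedule: "Patients were asked to assess their pain sensation and bleeding at 1st, 3rd, 7th 14th, 21st and 30th days". Colour is assessed at five visits, thickness before surgery and at 4 weeks, and a healing index is also recorded.

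For numerical data, the IV-Statistical analysis section uses two routes between groups. The parametric route reads "Parametric data were analyzed using one-way ANOVA followed by" Tukey's test. The non-parametric route is Kruskal-Wallis and then "pairwise comparisons utilizing Mann Whitney U test with Bonferroni correction for intergroup comparisons". Categorical data, which would include bleeding scored 0 or 1, get a chi-square test, with no pairwise step stated. The section is in the past tense: "Statistical analysis was performed with IBM® SPSS® Statistics Version 26 for Windows".

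**The concern.** A power figure belongs to one outcome, one effect and one test. Here the text leaves room for many: 6 + 6 + 5 + 1 = 18 outcome-visit results for pain, bleeding, colour and postoperative thickness, plus the healing index, and for each either the three-group test or one of three pairs. The question in the title is one of those pairs, and numerical pairs are judged after a correction that the sample size text does not mention.

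If the 80% belongs to the three-group test, it does not carry over to a single pair. If it belongs to an unadjusted two-group test, the corrected pair has less power at the same effect. At stake is how a null result is read. With both dressings better than gel foam, PRF and HA could easily fail to separate, and a reader might treat that as an adequately powered finding of no difference. The protocol makes the power claim itself, so the point cannot simply be passed to an unseen SAP.

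**Working it through.** **Inputs from the protocol.** Alpha 0.05, power 80%, 10 per group, three groups; Tukey, or Bonferroni over three pairs (0.05/3 = 0.0167). Effect, SD, outcome, sidedness and comparison are not printed.

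**Reproducing the stated figure.** For two means, n per group = 2(z₁₋α/₂ + z₁₋β)²/d², with d the difference in SD units. With no d, the figure of about 10 can be neither confirmed nor refuted. It can only be turned round: what does 10 per group detect with 80% power?

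- Normal approximation, two-sided: d = (1.960 + 0.842) × √(2/10) = 1.253.
- Exact two-sided t: P(|T| > 2.101) = 0.80 with 18 df and noncentrality d√(10/2) gives d = 1.325.
- Exact one-sided t: d = 1.156.
- Exact t at 0.0167: d = 1.574.
- Three-group F test (2 and 27 df, critical value 3.354, noncentrality 30f²): f = 0.600. The difference between the extreme groups is then 0.600 × √6 = 1.469 if the third group lies midway, or 0.600 × 3/√2 = 1.272 if one group differs from two equal ones (both from unrounded f).
- One pair under Tukey: the studentised range 3.506 gives a critical t of 3.506/√2 = 2.479 with 27 df, and 80% is reached at d = 1.496.

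**Power of the PRF-versus-HA pair under Tukey.** Normal data, 10 per group, P(|T| > 2.479) with 27 df and noncentrality d√5, not requiring a significant ANOVA first:

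| Assumed origin of n = 10 | PRF-HA difference (SD) | Power |
|---|---|---|
| One-sided t, unadjusted | 1.156 | 55% |
| Two-sided, normal approximation | 1.253 | 63% |
| Two-sided exact t, unadjusted | 1.325 | 68% |
| F test, HA equal to control | 1.272 | 64% |
| F test, control midway | 1.469 | 78% |
| t at the Bonferroni level 0.0167 | 1.574 | 84% |

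Requiring a significant ANOVA first lowers the unadjusted two-sided and F-test rows by at most about 1.5 percentage points in simulation. If 10 was rounded up from just above 9, the just-detectable d is 1.407 and the two-sided exact reading gives 74%.

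On the Mann-Whitney route, d = 1.325 with normal data gives 58% at 0.0167. Across the shapes and tie patterns tried, with d from 1.272 to 1.469, the range is 48% to 87%, so no single figure applies.

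**Where much lower figures come from.** Under the F-test reading, if HA gives 50% or 75% of PRF's benefit over control, Tukey power for PRF versus HA is 22% or 6%. The PRF-HA differences are then only 0.734 and 0.353 SD. An unadjusted two-sided t-test on the same 10 per group (critical value 2.101, 18 df, noncentralities 0.734√5 = 1.64 and 0.353√5 = 0.79) would have only 34% and 12%. Most of the drop from 80% is therefore the smaller effect, which no correction or wording causes. The cost of the correction itself is better seen in the two-sided exact row: 80% to 68%.

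**The case for a change.** The strongest argument for a change is that the claim is the protocol's own, that the group size is built on it, and that it cannot be checked. Depending on facts not stated, the same sentence can accompany 84%, 68% or 55% power for the title question, or far less if HA performs close to PRF. Rewording costs nothing beyond retrieving one calculation, and it would protect readers from over-reading a null result.

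Part of this stands. The text does not say what the 80% refers to, the arithmetic above is sound, and a fuller sentence would have been better reporting.

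The rest does not carry a change. The sample size section never attaches the 80% to PRF versus HA, so it does not contradict the corrected tests in the analysis section. The calculation is not free-floating either: it is tied to a cited study, whose inputs are referenced but not printed. Each shortfall depends on assumptions the documents do not settle: an unadjusted level, an effect just large enough, a choice of sidedness, and normal data for the Tukey figures. For bleeding the protocol states no corrected pair at all, so the concern as framed does not reach that outcome.

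**Conclusion.** No change to the plan follows. The gap is real but is one of reporting: the basis of the calculation is cited rather than written out. It is not shown that 10 per group is too few, or that a stated power is missed.

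For normal data under Tukey, 10 per group gives a pair at least 80% power when the true difference is about 1.5 SD or more. If the original calculation was unadjusted, two-group, and set at the effect it could just detect, the pair has about 68% (two-sided exact t) or 55% (one-sided). If it used a corrected level or a large enough effect, there is no shortfall on that route.

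The protocol describes recruitment and analysis as done. Spelling out the basis now would alter no patient number, test, correction, estimate or decision rule, and Tukey and Bonferroni are valid as they stand. What remains is ordinary care in interpretation, which needs no amendment: the 80% should not be assumed to cover the corrected PRF-versus-HA pair, and a non-significant result for that pair is not evidence that the two dressings are alike.

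### Is the Group II hyaluronic acid regimen left so open that the comparison with the gel-foam control loses its meaning?

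*Protocol*

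**What the plan says.** Three parts of the protocol describe what Group II received.

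- **Grouping Criteria, Group II:** hyaluronic acid "gel 3-4 times per day as a palatal dressing after free gingival graft harvesting". No end day is given. The corresponding line for the control arm reads "Patients received gel foam as a palatal dressing after free gingival graft harvesting".
- **IV-Surgical protocol, Group 2, step 4:** gel foam is cut to the graft's "dimensions to act as a carrier for the hyaluronic acid", and step 5 has it sutured in place. No reapplication is mentioned. In Group 3, step 4, the foam is cut to the graft's "dimensions and used as a palatal dressing", and step 5 fixes it with the same type of suture.
- **V-Postoperative care, for all arms:** patients are "instructed to avoid brushing at the surgical site only rinsing with hot saline mouthwash". Gel is not mentioned for any group.

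The footnotes on hyaluronic acid under Grouping Criteria and under the Group 2 steps name the same 0.2% oral gel.

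**The concern.** The regimen is one of the treatments named in the trial's title, and defining it is the protocol's job, so a separate analysis plan would not excuse a gap here. Taken one at a time, the sections seem to describe different treatments: a gel applied several times a day, a single placement on foam, and aftercare without gel.

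At stake is what Group II against Group III means. With the carrier alone, the two arms share foam and suture, and the contrast would be the hyaluronic acid product. With carrier and daily gel, repeated application is also part of the difference. With gel alone against foam, two things would differ.

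The missing end day makes the amount of exposure look wide open too. If the end day is assumed to be day 7, there are 3 × 7 = 21 to 4 × 7 = 28 applications. If it is day 30, there are 3 × 30 = 90 to 4 × 30 = 120. A reader could then ask whether the later outcomes, including mucosal thickness at 4 weeks, were measured during gel use or after it.

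**Working it through.** The question is one of text, so the check sets the sections side by side. The protocol's only design figure, about 10 patients per group, does not bear on it. No effect size or standard deviation is given with that figure, and nothing in it refers to how long gel was used.

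**1. Do the sections exclude each other?** Grouping Criteria is a short summary of each arm. The surgical section lists what was done in the operation. A list of operative steps has no reason to mention what is applied at home afterwards, so its silence on reapplication contradicts nothing.

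**2. Which readings survive the whole text?**

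| Reading of Group II | Grouping Criteria (gel several times a day) | Group 2 surgical steps (sutured foam carrier) |
|---|---|---|
| Gel only, no foam | fits | contradicted |
| Foam carrier only, no further gel | contradicted | fits |
| Foam carrier at surgery, then repeated gel | fits | fits |

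A sutured carrier cannot itself be applied three or four times a day, so the carrier-only reading leaves the stated frequency with nothing to refer to. Only the third row gives effect to both sections.

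**3. Do the postoperative instructions break that reading?** They tell the patient to rinse instead of brushing at the site. This is a hygiene instruction common to all arms. It does not forbid gel, and it need not repeat a treatment specific to one arm that is stated elsewhere.

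**4. Does suture removal define exposure?** The protocol says "sutures was removed after 1 week" but never connects that event to gel use. Pain and bleeding are recorded as "pain sensation and bleeding at 1st, 3rd, 7th 14th, 21st and 30th days". Counting how many of those visits fall after the first week therefore says nothing about who was using gel at the time.

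**5. Does any analysis depend on the end day?** The tests in the Statistical analysis section are chi-square, ANOVA or Kruskal-Wallis between groups, and repeated-measures ANOVA or Friedman within groups. They use group membership and visit. None takes the number or duration of gel applications as an input, so all can be run as written.

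**6. What does Group II against Group III estimate?** On the surviving reading it is foam plus the hyaluronic acid regimen against foam alone, with the same kind of suture and the same common aftercare. No placebo gel is described for Group III. Even a carrier-only regimen would therefore compare foam plus the gel product with plain foam. No reading separates hyaluronic acid from its gel base, so the choice between readings matters less to the interpretation than it first appears.

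**The case for a change.** The strongest reply is that joining the sections is the reader's inference. No sentence says that gel follows the carrier, who applies it or when it stops. A reader who wanted to repeat the treatment could not do so from this text, and the intervention is protocol content. Asking for clarification would cost only some wording and a look at the records of 10 patients.

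Most of that stands as a comment on reporting. The end day is missing, and the daily schedule is not expressly tied to the foam.

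It does not stand as a fault in the plan. The step from there to conflicting conclusions relies on readings that the protocol's own text rules out. The totals of 21 to 120 applications come from assumed end days and measure no effect on any result. Whether thickness at 4 weeks was taken during or after gel use affects how the result is described. It does not affect the validity of comparing the groups as randomised.

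**Conclusion.** The concern does not call for a change. The sections are compatible, and the plan as written gives a valid randomised comparison of a hyaluronic acid regimen on foam with foam alone. The gap is one of description: the duration of gel use is unstated, and the link between daily gel and the sutured carrier is left implicit. Its effect on any estimate, error rate or power is not shown, and the document offers nothing from which to calculate one.

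This rests on two assumptions: that the Grouping Criteria and the surgical steps were both meant to hold for Group II, and that patients were treated accordingly. Because the protocol is written in the past tense, the natural remedy lies in the write-up. It should reconcile the three sections in one description, report from existing records what Group II received and for how long, and word the conclusion as being about the regimen as given. This review takes no view on what that regimen should be.

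### No masking is stated for the ImageJ colour reading or the healing index, so an observer shift could pass for a benefit of the active dressings over gel foam; the colour photographs can be read masked at little cost

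*Protocol*

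**What the plan says.** Under III- Assessments, Objective assessment, the Protocol compares the colour of the palatal mucosa with the adjacent and opposite side by "taking pictures and using the image J program at 3rd, 7th, 14th, 21st and 30th days". Section VI repeats this. Neither place says who takes or measures the photographs, how the regions are chosen, or whether the reader knows the arm.

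The same sections say that a published healing index "was used to assess the palatal wound healing". Of its components, "tissue color, response to palpation, presence of granulation tissue presence of suppuration and epithelization of the incision margin were recorded". No assessor, masking or assessment days are given for the index.

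The only related safeguard is under Grouping Criteria: "Allocation concealment was achieved using a sealed coded opaque envelope containing treatment of the subject".

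Section IV, Surgical protocol, describes the dressings:
- Group 1: "The PRF membrane was placed as a palatal dressing and fixed in place by X suture using 5-0 polypropylene".
- Group 2: "Gel foam was cut according to the graft's dimensions to act as a carrier for the hyaluronic acid".
- Group 3: "Gel foam was cut according to the graft's dimensions and used as a palatal dressing".

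Under V-Postoperative care, "sutures was removed after 1 week".

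**The concern.** Concealment before assignment prevents selective enrolment. It has no effect once the dressing is in place and the outcome is being read. Masking of assessors is a design feature that a protocol should fix, so the fact that no SAP is at hand does not explain its absence.

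Both outcomes leave room for judgement. The healing index grades colour, granulation and epithelization by observation. ImageJ returns a number, but that number depends on which part of the wound and which reference area the reader outlines. A reader who expects the active dressings to do better could move either result in their favour. None of the tests listed in the Statistical analysis section can separate such a shift from a treatment effect.

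**Working it through.** **1. The plan's own figure.** Grouping Criteria states about 10 patients per group at alpha 0.05 and 80% power. This cannot be reproduced, because the protocol gives no effect size or SD. Solved backwards, a two-sided comparison of two means (normal approximation) gives d = (1.960 + 0.842) × √(2/10) = 1.25 SD. For the three-group ANOVA, 10 per group corresponds to Cohen's f = 0.60. These values serve only as a yardstick below.

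**2. Inputs for the illustration.** From the Protocol: three groups of 10, one-way ANOVA for parametric data, significance level 0.05. Assumed: no true effect, and an observer shift of b SD in favour of both active arms. The documents give no value for b, so a range is shown.

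**3. Formula.** The arm means are b, b and 0, with grand mean 2b/3. The squared deviations sum to (b² + b² + 4b²)/9 = 2b²/3. Hence f = √(2b²/9) = 0.471b, and the noncentrality is λ = 10 × 2b²/3 = 6.667b². The rejection rate is the probability that a noncentral F with 2 and 27 degrees of freedom exceeds the 5% critical value, 3.354.

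| Assumed shift b (SD) | f | λ | Rejection rate |
|---|---|---|---|
| 0 | 0 | 0 | 5.0% |
| 0.25 | 0.118 | 0.417 | 7.9% |
| 0.5 | 0.236 | 1.667 | 17.8% |
| 0.75 | 0.354 | 3.750 | 35.5% |

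A simulation of the same setting gave 8.5%, 18.1% and 35.8% (4.7% with no shift), in line with the exact values. All three assumed shifts lie well below the f of 0.60 that the trial is sized to detect.

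**4. Which contrast this concerns.** The bias is b − 0 = b for each active arm against gel foam. For platelet rich fibrin against hyaluronic acid it is b − b = 0. The table therefore says nothing about the comparison named in the trial's title.

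**5. What the photographs can mask.** They are specified for colour, on days 3, 7, 14, 21 and 30. Sutures come out after 1 week, so on day 3, and possibly on day 7, the dressing and its sutures may still be visible. A fibrin membrane may then look different from gel foam; Groups 2 and 3 both have gel foam and are harder to tell apart. This is an inference from the surgical steps. Days 14, 21 and 30 fall after suture removal. The healing index includes response to palpation, which needs a live examination, and no photograph schedule is attached to it.

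**The case against.** The strongest reply is that silence is not evidence. A reader might infer that the assessors knew the arm. The protocol does not say so; it says nothing on who assessed or what they knew. That reply stands, and the point is limited to this: masking is not stated, so the plan as written does not secure it.

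A second objection is that the magnitude rests on assumed shifts, uses an ANOVA that applies only to data treated as parametric, and leaves the title comparison untouched. All of this is right. The percentages illustrate sensitivity and do not estimate bias in this trial. A Kruskal-Wallis test would not remove an observer shift either, but its rejection rate was not calculated.

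A third is that ImageJ leaves less room for judgement than a clinical score, and that heading these outcomes as objective merely separates them from patient-reported ones. Both are fair. The heading is no error, and the remaining discretion in ImageJ lies mainly in choosing regions.

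Finally, a reader might suppose that coded photographs would mask the healing index too. They would not, because of palpation. Scoring only its visible components would split the index. A separate masked examiner would be an added resource and is not asked for here.

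**Conclusion.** The concern holds in a limited form. The protocol describes no masking for the colour reading or the healing index, and its one safeguard ends at assignment. An observer shift could therefore produce an apparent benefit of the active dressings over gel foam. Under assumed equal shifts of 0.25, 0.5 or 0.75 SD in both active arms and no true effect, the false-positive rate of the F test rises from 5% to about 8%, 18% or 36%.

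The documents do not support the stronger readings that outcomes were in fact read with the arm known, that a bias of this size is present, or that these rates apply to platelet rich fibrin versus hyaluronic acid. The point merits correction because, for colour, the remedy uses photographs the plan already takes.

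**What to change.** **Colour.** Add a paragraph to the Objective assessment section stating that:
- patient, arm and day are stripped from the photographs, which then receive random codes and are shuffled;
- the rule for selecting the wound, adjacent and opposite regions is fixed before any file is read;
- all files are read in ImageJ after the last day-30 visit, and the key is withheld from the reader until the readings are locked;
- days 14, 21 and 30 are the masked readings, while days 3 and 7 are reported as possibly unmasked.

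**Healing index.** Report it as assessed without stated masking, and interpret differences between the active dressings and gel foam accordingly.

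**Cost.** Renaming and shuffling files, a written region rule and one paragraph of text, with no extra visit, procedure or reader. The protocol is written in the past tense; if visits are complete, retained photographs can still be coded and re-read. The downsides are that readings are batched at the end, early images stay partly recognisable, and a reader who treated the patients may still recognise some images.

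### The blood draw that only Group 1 has comes before baseline palatal thickness and graft harvest, so membership of Group 1 must be known to someone on the team before either

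*Protocol*

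**What the plan says.** Under Grouping Criteria the Protocol describes concealment: "Allocation concealment was achieved using a sealed coded opaque envelope containing treatment of the subject". It does not say when the envelope is opened or who opens it.

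Under IV-Surgical protocol, B) Surgical procedures, the steps are numbered separately for each group. Group 1, after palatal anaesthesia at step 1, has at step 2: "Just prior to surgery a 10 ml intravenous blood was obtained from the median antecubital vein". Centrifugation, clotting and preparation of the membrane follow at steps 2 to 4. Only then come the baseline reading, "The thickness of the palatal tissue was measured at three different points" (step 5), and the harvest, "Free gingival graft was harvested from the palate and its thickness was measured" (step 6). In Groups 2 and 3 the same two actions are steps 2 and 3, directly after anaesthesia, and no blood is taken.

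No target length, width or thickness is given for the graft; in Groups 2 and 3 the gel foam is trimmed to match whatever was taken. Under III-Assessments, palatal thickness is an outcome measured before surgery and again at 4 weeks with a graduated probe. No separate or masked operator or assessor is described.

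**The concern.** Concealment protects the decision to enrol. It does nothing for measurements and surgical choices made after the allocation has been read. Two such items here feed the comparison between arms.

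- **Baseline thickness.** The preoperative reading is one half of the thickness outcome and is taken by hand.
- **The wound.** The extent and depth of the harvest define the wound whose pain, bleeding, healing index and colour are compared, and the operator is not held to a stated size.

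If the person who probes or cuts knows that a patient is in Group 1, either item can drift with the arm without anyone intending it. Analysis cannot fully undo this: adjusting for a baseline that was itself read with knowledge of the arm carries the error along.

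**Working it through.** The point rests on sequence, not on a figure in the plan, so the check is to set the numbered steps side by side.

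| Action | Group 1 | Group 2 | Group 3 |
|---|---|---|---|
| Palatal anaesthesia | step 1 | step 1 | step 1 |
| Blood draw and membrane preparation | steps 2-4 | none | none |
| Baseline thickness, three points | step 5 | step 2 | step 2 |
| Graft harvest and graft thickness | step 6 | step 3 | step 3 |
| Dressing placed and sutured | step 7 | steps 4-5 | steps 4-5 |

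1. Blood is drawn in one arm of three. Whether to draw depends on the allocation, so for all 30 patients someone must know the answer to 'Group 1 or not' before that point.
2. The timing of the draw is loosely worded: it is numbered after anaesthesia but described as just before surgery. On either reading it precedes steps 5 and 6.
3. Steps 1 to 3 are the same in Groups 2 and 3. For those 20 patients the order requires only the knowledge that they are not in Group 1.
4. In every arm the relative order is anaesthesia, thickness, harvest, dressing. The only difference is what is interposed in Group 1.

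**Size.** The document gives nothing from which to estimate a shift. The following is a pure assumption, shown only for scale. Suppose knowledge of Group 1 moved that arm's outcome directly by b standard deviations, with 10 patients per arm, no true effect, and a three-group one-way ANOVA at 0.05 (critical F on 2 and 27 degrees of freedom = 3.354). The noncentrality is 10 × b² × 2/3.

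- b = 0.25: noncentrality 0.417, rejection 7.9%.
- b = 0.5: noncentrality 1.667, rejection 17.8%.

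If instead the drift is in graft size, and graft size correlates 0.3 with the outcome (also assumed), the outcome shift is 0.3 × 0.25 = 0.075 to 0.3 × 0.5 = 0.15 standard deviations.

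- b = 0.075: noncentrality 0.0375, rejection 5.3%.
- b = 0.15: noncentrality 0.15, rejection 6.0%.

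So the answer runs from almost nothing to more than three times the nominal 5%, depending wholly on the inputs assumed.

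**The case against.** The case against is substantial and part of it stands.

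- **Knowledge by someone is not knowledge by the operator.** A separate person could open the envelope and draw the blood. That is possible, but no such person is described, and the draw is numbered after palatal anaesthesia, when the operator would probably notice it.
- **The routes to bias are narrow.** The three probing points are at fixed landmarks, 7 mm from the gingival margin, and the needs of the recipient site plausibly limit how large a graft is cut. Graft thickness is recorded in every arm, so an imbalance in wound depth can be checked. This stands as mitigation. Recording of wound area is not stated.
- **This overlaps with the absence of described masking in general.** It does, but the order of steps is a distinct part that can be put right even where full masking of surgery is not feasible.

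A reader might infer that the full allocation is known to the operator in every patient before harvest. The documents do not support that: the time of opening is inferred, and nothing in the sequence requires Group 2 to be distinguished from Group 3 by then. A reader might also infer that the false-positive rate is 8-18%. That range assumes a direct shift in the outcome, for which the Protocol gives no basis.

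**Conclusion.** The point holds in limited form. The written order puts an action specific to Group 1 ahead of the baseline reading and the harvest, so Group 1 status must be known to someone on the team before both. This is an opportunity for arm-related drift in the baseline thickness and in wound size. It is not evidence that drift occurred, and neither its direction nor its size can be derived from the document. Concealment up to enrolment is not shown to be broken.

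The conclusion assumes that the numbered steps were carried out in the order written and that blood was drawn only in Group 1, as listed. It is a cheap improvement worth making, not a flaw that invalidates the comparison.

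**What to change.** Use one order in all arms up to allocation:

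1. Measure and record the three palatal thickness points.
2. Record the planned graft outline and intended thickness.
3. Open the envelope, noting the time and who opened it, and then follow the arm-specific steps.
4. In the report, compare planned with harvested graft dimensions by arm, using the graft thickness already recorded.

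If patients have already been treated, report when and by whom envelopes were opened, and tabulate baseline thickness and recorded graft thickness by arm.

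**Cost.** One added case-form entry, and a somewhat later blood draw and 10-12 minute spin in Group 1. How these are timed relative to anaesthesia is for the investigators to settle. No blood is taken from the other arms. The harvest itself remains unmasked, because the envelope is still opened before the graft is cut. The change makes the baseline reading independent of the allocation and puts the surgical intention on record, and it achieves no more than that.
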